Recruitment and Consent of HIV+ Couples: Couples who test positive for HIV during an ANC visit at one of the study sites will be asked whether they would be willing to participate in a research study. If the couple is interested, they will be provided a consultation with the study coordinator, at which point they will be asked to give informed consent through our consent form. This consent will include their willingness for us to access medical records and participate in survey sessions.

Participant confidentiality

All participants who are consented in the study will be assigned a study ID number. Only study members will have the codebook that links the identifiers. Identifying information associated with these ID codes, such as names, will be kept in a data file separate from the survey data and clinic records. All data will be managed in a way that meets Vanderbilt IRB and Mozambique Bioethics standards for the protection of human subjects and to ensure confidentiality and the protection of sensitive health information.

A participant's study information will not be released without the written permission of the participant. All study-related information will be stored securely at the study site. All participant information will be stored in locked file cabinets in locked rooms, i.e., access is limited to study staff. All study data collection, process, and administrative forms and other reports will be identified by a coded number to maintain participant confidentiality. All records that contain names or other personal identifiers, such as locator or informed consent forms, will be stored separately from study records identified by a code number. All databases will be secured with password-protected access systems. Forms, lists, logbooks, appointment books, and any other listings that link participant ID numbers to other identifying information will be stored in a separate, locked file in an area with limited access.

Consent Procedures

The consent procedures are detailed above and the consent form can be found in the annex (Appendices 4 and 5). The signed consent forms will be kept in a lock box at the FGH office in Quelimane, separate from the transcripts of the interviews. The consent forms will be kept for 7 years, at which point they will be burned to ensure that no one will be able to link any consents to participants.

Evaluation of benefits and risks

Adverse events

Risks to the subjects (both intervention and control group): The level of risk associated with this research is expected to be minimal for all participants. Potential psychological discomfort may occur when administering the survey as many of the questions are personal and have to do with

a stigmatized infectious disease. Participants are able to decline to answer any question that they deem uncomfortable.

Participants who enroll in couples HIV care and treatment will have the potential for interpersonal conflict, given that they will receive their care and treatment together. To mitigate this concern we are providing couples based counseling at the facility and peer support in the community.

Adverse Experience: We do not anticipate any adverse events as a result of this study, however study participants will be provided with a telephone number and instructed to contact study clinicians to report any serious AEs they experience.

Protection against risks: The study protocol and training manuals will include strict guidelines for conducting the survey and recording the data in a confidential manner. All study staff will receive formal responsible conduct of research training per NIH, Vanderbilt, and Mozambican Ministry of Health guidelines. Participants may withdraw from the study for any reason at any time.

Benefits

For HIV-infected couples there is a possibility that couple-based HIV care and treatment will result in them gaining additional psychosocial support and education for their HIV treatment. For these patients, they could experience improved health outcomes. The results of this evaluation may help us to offer better services for HIV-infected couples living with HIV who access services at the study clinics and throughout Mozambique. This could benefit Mozambican society through improved health programs for people living with HIV.

12. Limitations

Given the cluster RCT design, inter-clinic contamination is possible but will be eliminated by selecting geographically isolated clinics >1.5 hour driving distance apart where patients very rarely visit both clinics.

13. Dissemination Plan

Results from this study will be collected into a report, and will be shared with MISAU and the DPS. The results will also be disseminated to government officials and physicians working in these communities. If results are deemed by the authors to be potentially of interest to a wider scientific audience, we would plan on sharing these data in manuscript form, after obtaining appropriate clearances.

14. Budget

Description	TOTAL USD	MZM	Study Details	
Human Resources	60,000	4,200,000	Price per unit/person	Number of people/units
Project Officer (TBD)	30,000	2,100,000	30,000	1
Study Assistants	30,000	2,100,000	1,250	24
TRAVEL & TRANSPORT	14,670	1,026,900		
maintenance for car/gas (per day 44USD)	6,750	472,500	\$45	150
cell support for study assistants	2,880	201,600	10	24
basic nokia phone for each study assistant	960	67,200	40	24
bicycle repair kit	720	50,400	30	24
bicycles for peer supporters	3,360	235,200	140	24
TRAINING/PROJECT ACTIVITIES	5,980	418,600		
Training for Peer supporters				
per diem (food)	2,880	201,600	15	96
Venue hire	1,100	77,000	50	12
Training Materials	2,000	140,000	2,000	1
OTHER	2,500	175,000		
Laptop and accessories for Project Officer plus internet via movital	2,000	140,000	140,000	1
Photocopies of consent forms and questionnaire	500	35,000	0.25	
Total of all costs	83,150	5,820,500		
Contingency 10%	8,315	582050		
TOTAL	91,465	6,402,550		

15. Timeline

	Year 1	Year 2	Year 3	Year 4	Year 5
Version 2					

Study Activities	1	2	1	2	1	2	1	2	1	2
Staff and counselor hiring and (re)-training										
Enrollment of pregnant women & partners										
3, 6 , 12, and 18 month follow up										
Survey collection										
Fidelity assessments										
CEPAC model expansions										
Last study participant visits										
Data collection & management										
Data analysis										
CEPAC model inputs from trial data										
Model-based cost-effectiveness analyses										
Manuscript preparation										

Timeline of Study Activities

16. Bibliography

1. INSIDA: **National Survey on Prevalence, Behavioral Risks and Information about HIV and AIDS (2009 INSIDA)**. In. Maputo, Mozambique: Instituto Nacional de Saúde (INS), Ministry of Health (MISAU), & Instituto Nacional de Estatística (INE); 2009.
2. Ministerio da Saude (MISAU), Instituto Nacional de Estatística (INE), ICF International (ICFI): **Moçambique Inquérito Demográfico e de Saúde 2011**. In. Calverton, Maryland, USA: MISAU, INE e ICFI; 2013.

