Our proposed research builds on a 4-year pilot intervention that developed a community-based strategy to engage male partners in the ANC services of their wives in rural Mozambique. **Homens para Saúde (HoPS) – (“Men for Health”)**, deployed respected men as community health workers and Traditional Birth Attendants (TBAs) to provide community-based counseling and accompany couples to ANC/HIV testing, and led to substantially improved service uptake within two years. In our new project, **“HoPS+”, we will implement a novel partner-based ART enrollment immediately when both partners receive simultaneous HIV diagnoses in ANC.** Our intervention will create an integrated structure to provide couple-based ART within comprehensive HIV care and treatment services. Anchored on professional and peer couples counseling, this intervention will ensure that partners are engaged and retained in care throughout pregnancy and the post-partum period.

5. Objectives

The overall goal of this project is to develop and assess the impact of a partner-based ART delivery intervention among HIV-positive expectant couples.

Our specific objectives are as follows:

Objective 1: To implement, monitor, and evaluate the impact of couple-based services on retention in care, viral suppression, and early infant diagnosis (EID) among HIV+ pregnant women and their HIV+ male partners through a cluster RCT. Implementation process variables will be collected (number of expert-couple counseling sessions, adherence to content, and evaluation of participant and peer experiences).

Objective 2: To investigate the impact of the HoPS+ intervention on hypothesized mechanisms of change.

We will determine the intervention's impact on hypothesized mechanisms of change, including (1) partner social support;^[45] (2) HIV stigma;^[46] (3) relationship empathy ^[47](4) HIV knowledge;^[48] and (5) patient trust in provider^[49] through quantitative surveys with patients at baseline and 6 months.

Objective 3: To use validated simulation models to evaluate cost-effectiveness of the HoPS+ intervention.

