This study is important because it targets the health and well-being of the mother-infant-male partner triad,^[50] the essential family group that has eluded effective engagement strategies in HIV care. It builds on our research team's extensive experience in: (1) HIV care and treatment; (2) male partner engagement; (3) and cost-effectiveness analysis. Our results will improve outcomes by effectively engaging couples in HIV care and treatment during pregnancy and beyond. Without effective innovation in culturally appropriate adherence support to all stages of the care continuum, EMTCT efforts will fail in rural Africa.

6. Design and Study Questions

We propose to conduct a matched-pair cluster Randomized Controlled Trial to evaluate the effects of our intervention. To our knowledge, this is the first ANC-based couples study that will assess definitive treatment outcomes within a randomized controlled trial (RCT), and analyze the cost-effectiveness of the intervention. Twenty-four primary and secondary level health care facilities in Zambézia Province will be matched and then randomized to the control (standard-of-care [SOC]) or intervention (HoPS+) arms (12 sites per arm). We opted for a study design in which the unit of randomization is the EMTCT clinic (not the individual) because it would be extremely difficult to implement the intervention to only a subset of clients within each facility. We will match clinics on ART uptake rates, retention in care among patients on treatment, patient volume, HIV prevalence in ANC, and level of facility (secondary or primary)^[51] using reweighted Mahalanobis distances^[52] and then randomize clinics in each matched pair to intervention and SOC arms – 12 clinics per arm, 24 total. Intervention and control sites will be >100 km of each other to prevent contamination.

There are four specific study questions:

Question 1: Is our intervention idea (partners-based ART services for expectant and post-partum couples) acceptable to expectant couples?

Question 2: Does our intervention positively impact partner support for ART medication adherence and retention in care? Does it increase empathy among partners enrolled? Does it increase knowledge about HIV? Does it reduce HIV stigma among couples enrolled into the intervention?

Question 3: Does our intervention improve the proportion of exposed infants who are tested for HIV (early infant diagnosis)? Does it decrease the number of infants who are HIV-positive at 12 months?

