Question 4: Is the intervention cost-effective? Would the Ministry of Health be willing to scale it up based on our costing data?

7. Study Population

a. Population:

Couples consisting of two adults 18 years or older (one HIV-infected pregnant woman and her HIV-infected male partner) presenting for ANC services together at one of 24 clinical sites in Zambézia province.

b. Inclusion Criteria:

Couples, one HIV+ pregnant woman and her infected male partner, will be eligible to participate if the woman's due date is >2 weeks from enrollment. Both persons must also be 18 years or older, able to give consent, willing to consent to an infant record search, and must agree to enroll in ART together.

c. Exclusion Criteria:

Couples will not be eligible to participate in the study if the woman is not pregnant, if both persons are not HIV+, if either person is younger than 18 years, if one member of the couple is unwilling to enroll in ART or consent to the infant record search, or if one member of the couple is unable to give consent due to mental limitations.

d. Calculations of Sample Size:

Objectives 1 & 3: With 24 clusters and 45 couples per cluster, we have over 80% power to detect a 30% increase in the proportion of pregnant women who initiate ART from 55% to 71.5% with $\alpha = 0.05$. Our power calculations count adults and babies who dropout during the EMTCT cascade (e.g. do not initiate ART) as failures for downstream aims (e.g. retention on ART or viral suppression). For example, SOC ART retention was calculated as the proportion of women who initiated ART multiplied by the proportion of women retained in care ($0.55 \times 0.56 = 0.31$). In our sample size calculation, we power for a 20% increase in adult ART retention (above and beyond the 30% increase in adult ART initiation, for an improvement in retention from 31% to 48%), 90% vs. 80% viral suppression among women or men, 20% increase in EID testing, and 40% reduction in infant HIV positivity. Women, men and infants will be evaluated as separate study populations.

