Couples in the intervention and SOC arms will be consented into the study immediately after testing positive for HIV through couples counseling at an ANC appointment. Enrollment will be completed by a study assistant based at the site. A similar enrollment protocol in Zambézia has yielded study enrollment >95% immediately after an HIV test is completed; so we anticipate few recruitment problems. Patient management and monitoring forms will be completed for all HIV-infected couples enrolled in the study. Select demographic, clinical and laboratory data from these forms will be routinely entered into the OpenMRS electronic medical record system (EMR) at FGH-supported sites. OpenMRS data are managed by the FGH data manager who identifies discrepancies, works with sites to resolve them, and updates the database accordingly.[53]

Standard-of-care services (SOC) (Objectives 1 & 2):

The 12 clinics randomized to the **control arm** will continue to provide SOC EMTCT services that include: standard HoPS male engagement (male invitation to ANC services and couples HIV testing), opt-out rapid HIV testing of all pregnant women attending ANC, HIV-specific counseling and support for all women who test positive, provision of cotrimoxazole prophylaxis, and universal

Figure 1: Procedures in Standard of Care vs. Intervention

ART, as per option B+ guidelines (Figure 1).[4] Couple as well as relevant medications are also offered free of charge in the HIV clinic to male partners. Post-partum women and their exposed infants continue EMTCT follow-up, after delivery, at the EID clinic in a “one-stop point of care model”. Post-partum women continue their HIV care and treatment follow-up, including provision of cotrimoxazole prophylaxis, and counseling and support; infants have access to HIV testing by dried blood spot (DBS)-PCR as early as 4-6 weeks after birth,. Follow-up at the EID clinic for both mother and infant continues for 18 months, unless an infant is diagnosed HIV positive and referred to HIV treatment services (Table 2).

Intervention arm: “*Homens para Saúde +*” (HoPS+) – (Men for Health+) (Objectives 1 & 2):

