Objective 2: Individuals consented in the study will complete interviewer-assisted, quantitative study measures at baseline and by 6 months post-study enrollment, including measures of: 1) partner social support;[45] (2) HIV stigma;[46] (3) empathy [47]; (4) HIV knowledge;[48] and (5) patient trust in provider.[49]

Objective 3: Clinical outcomes of the linked models include MTCT risk at birth and weaning, pediatric life expectancy from birth, maternal and paternal life expectancy from presentation to care, and combined (maternal + paternal + pediatric) life expectancy. Economic outcomes, from the healthcare system perspective, include antenatal and postnatal program costs, lifetime maternal HIV-related healthcare costs, lifetime pediatric healthcare costs, and 1 to 5-year maternal and pediatric health care costs. We will use these outcomes to calculate incremental cost-effectiveness ratios (ICERs) in \$/life-year (LY) as the difference in combined healthcare costs (program + maternal lifetime + paternal lifetime + pediatric lifetime costs) between the two strategies, divided by the difference in combined projected life expectancy (maternal + paternal + pediatric life expectancy). For ICERs, all outcomes will be discounted at 3%/year.[79-81] We will consider a strategy to be "cost-saving" if it leads to greater combined life expectancy and lower combined costs than an alternative strategy. Following WHO guidance and evolving consensus in the field of cost-effectiveness analysis, we will consider a strategy to be "cost-effective," compared to its alternative, if its ICER is <0.5-1.0x Mozambique *per-capita* gross domestic product (GDP: \$525 in 2015)/LY. Recognizing the limitations of this approach, we will also compare ICERs to other HIV interventions in Africa, e.g., first line ART (\$500-\$5,500/LY).[82-86]

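### Question 1 asks whether partner-based ART is acceptable to expectant couples, but data are planned only on couples who have already agreed to start ART together

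*Combined protocol and SAP*

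**What the plan says.** Section 6 lists four study questions. The first is "Is our intervention idea (partners-based ART services for expectant and post-partum couples) acceptable to expectant couples". It carries no restriction to participants. Question 2, by contrast, speaks of enrolled partners and couples.

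Eligibility is set in section 7. Under 7b both partners "must agree to enroll in ART together". Under 7c a couple is excluded "if one member of the couple is unwilling to enroll in ART or consent to the infant record search". Both criteria apply in both arms.

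Section 8a sets the timing: "Couples in the intervention and SOC arms will be consented into the study immediately after testing positive for HIV". It then sets the coverage of the records: "Patient management and monitoring forms will be completed for all HIV-infected couples enrolled in the study". Section 8b does the same for the scales: "Individuals consented in the study will complete interviewer-assisted, quantitative study measures at baseline and by 6 months post-study enrollment". Those scales measure partner support, stigma, empathy, HIV knowledge and trust in the provider.

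The nearest thing to an acceptability measure is in section 5, Objective 1, where the process variables include "evaluation of participant and peer experiences". The data analysis part of section 10 covers Objectives 1 to 3 and gives no endpoint, denominator or analysis for Question 1.

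**The concern.** The population in the question is wider than the population with data. A couple that rejects starting ART together leaves at eligibility, before any form or scale is completed, and the readable text describes no count of such couples and no record of their reasons. Whatever the trial later says about acceptability comes from couples who passed the first test of it.

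This matters because male involvement is the uncertain step in this setting. The protocol's background says that community norms discourage men from taking part in antenatal care, and that fewer than 10% of HIV-infected partners identified in ANC enrolled on ART. That figure is routine programme uptake, not a refusal rate for joint ART. It does show that a high acceptance rate at entry cannot be taken for granted. If enrolled couples report good experiences, a reader could take that as the view of expectant couples in general, and the trial would have no data with which to qualify it.

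**Working it through.** The plan states no figure for acceptability, so there is none to reproduce. The check has two parts.

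**1. Population asked about against population observed**

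- Asked about (section 6, Question 1): expectant couples, with no enrolment limit.
- Admitted (7b, 7c): couples in which both partners agree to enrol in ART together.
- Observed (section 5, 8a, 8b): participants and their peers, enrolled couples, consented individuals.
- Couples who decline: section 11 describes what follows if a couple is interested, and nothing for those who are not. The figure in section 7e was not available for this check; no readable text mentions a screening or refusal log.

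**2. How large the gap could be**

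Let *a* be the share of approached, otherwise eligible couples who agree to joint ART, *s* the share of enrolled couples who find the service acceptable, and *r* the same share among decliners. Then

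- acceptability among all approached: A = a·s + (1 − a)·r
- overstatement: s − A = (1 − a)(s − r), which cannot exceed 1 − a
- couples not seen: 1,080/a − 1,080, where 1,080 = 24 clinics × 45 couples (section 7d)

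Inputs: *a* is an assumption, because the plan does not record it. The closest figure is in section 8a: "A similar enrollment protocol in Zambézia has yielded study enrollment >95% immediately after an HIV test is completed". I take a = 0.95 from that and a = 0.80 as an assumed less favourable case. For illustration s = 0.90 (assumed) and r = 0 (assumed: every decliner finds joint ART unacceptable).

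| a | A = a × 0.90 | s − A | ceiling, 1 − a | couples not seen |
|---|---|---|---|---|
| 0.95 | 85.5% | 4.5 points | 5 points | 1,137 − 1,080 = 57 |
| 0.80 | 72.0% | 18 points | 20 points | 1,350 − 1,080 = 270 |

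(1,080/0.95 = 1,136.8, rounded up to 1,137.) Section 7e gives 40 couples per site rather than 45. That would scale the counts by 40/45 and leave the percentages unchanged.

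**The case against.** The strongest reply is that the entry condition is not the intervention. Control couples also agree to start ART together and then receive separate services (section 7f). HoPS+ goes well beyond that: joint care, couple-centred post-partum treatment, six counselling sessions and about nine peer meetings (section 8a). Enrolled intervention couples can still reject most of it. The plan collects the number of expert-couple sessions and participant experience (section 5) and documents discontinuation, including by patient choice (section 7f). **This stands.** A reader might infer that Question 1 cannot be answered at all. The documents do not support that: it can be answered conditionally on agreement at entry.

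A reader might also infer that the trial will report 100% acceptance. No section defines acceptability as agreement at entry, so that is not a planned statistic.

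Nor do the documents show that the answer to Question 4 is inflated by this route. That question turns on costing data, and the model inputs in section 8b are cascade steps, biological parameters and costs, with no acceptability input.

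Two further points stand in part. Enrolment above 95% under a similar protocol suggests a small effect, but that protocol is not stated to have required joint ART, and this trial would not show whether the rate carried over. The programme also holds data from before enrolment: section 8b plans inputs on earlier cascade steps, and section 9 counts HIV-infected men identified through couples counselling. Neither is described as a couple-level record of refusals.

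Finally, the word together appears only in 7b. The exclusion in 7c also covers refusal of any ART and refusal of the infant record search, and neither of these shows that couple-based delivery is unacceptable. The remedy has to keep them apart.

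**Conclusion.** The concern holds in a limited form. As written, the plan can judge acceptability only among couples who already agreed to start ART together, whereas Question 1 is worded for expectant couples. Acceptance of the later components remains observable within the enrolled group.

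The size is unknown. The overstatement is at most about 5 percentage points if the earlier enrolment rate carries over, and up to 20 points at an assumed 20% refusal. Those ceilings are reached only if every enrolled couple finds the service acceptable and no declining couple does. Declining for other reasons, such as the record search, would make the gap smaller.

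No treatment-effect estimate depends on this point. It concerns whether a stated study question is answered in the right denominator, and it is worth correcting because the correction is cheap.

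**What to change.** During enrolment, have the study assistant at each site keep an anonymous tally of all otherwise eligible adult HIV-concordant couples approached, in these categories:

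- agreed;
- declined any ART;
- willing to take ART but declined joint ART;
- declined only the research or the infant record search;
- with the reason given for any refusal.

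At the 12 intervention clinics, report Question 1 as the share accepting joint ART among couples offered it, with an interval that allows for clustering by clinic. Show research-only refusals and refusals of any ART as separate categories, and state in advance how each enters the denominator. Report experience among enrolled couples separately and label it conditional acceptability.

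If the tally cannot be kept, reword Question 1 to refer to enrolled couples and add the limitation to section 12, which at present discusses only contamination between clinics.

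Cost: one tally sheet per site, a sentence or two in the protocol, and a few minutes of study-assistant time per couple. Eligibility, treatment and the other analyses are unchanged.

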Objective 2: Aim 2 analyses will utilize a subset of the 1,080 enrolled couples (2,160 individuals) who are alive and can be contacted to provide data by 6 months after enrollment, regardless of whether or not they are retained in care. Because the psycho-social data collected by 6 months may be influenced by whether or not participants were retained through 6 months, our analyses will initially only consider retention outcomes after 6 months to maintain the temporal order needed to infer any mediation effects.

e. Sampling

Participants: HIV infected couples will be enrolled for 6 months at each study site. Patients will be enrolled on a first come, first enrolled basis until 40 couples have been enrolled.

[figure not shown]
f. Patient participant retention and withdrawal:

As per standard clinic procedure, couples on the control arm will receive separate clinical services at the ANC building and the adult HIV clinic, respectively. Peer educators will track all clients who miss appointments at control and intervention sites. The Home Based Care workers will document clients as terminating care if they: (1) discontinued services due to death; (2) transferred their care to another clinic that is not in the study; (3) are lost to follow-up (defined as being >90 days late for a clinic appointment plus 3 failed attempts at tracking the client); or (4) discontinue for any other reason, including patient choice. Clients will not receive any remuneration for participating in the study, per Mozambican National Medical Ethics Committee, but interview participants will be provided a small snack. Clients will be allowed to discontinue participation and may decide that their medical data cannot be used in the analysis at any time during the study.

8. Methods

a. Study Procedures

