For this project, de-identified data will be extracted into a restricted dataset by FGH employees from the existing OpenMRS databases and sent to a VUMC Biostatistician for analysis. All routine programmatic data are owned by the MOH. All routine programmatic data are part of the clinical record and as such will not be destroyed.

Data Analysis

Objective 1: Statistical analysis plan for Objective 1. We propose a generalized linear mixed effects model, with random effect for clinic.[88] A simple model for $E(Y_{ij})$, the probability of ART initiation in the i th clinic at the j th time-point is given by:

$$\text{logit } E(Y_{ij}) = \beta_1 + \beta_2 \text{Group}_{ij} + b_i + e_{ij}$$

where b_i is a random effect for clinic i which accounts for clustering of patients within clinics, due perhaps to similarities in health-seeking behavior and/or access to care. β_1 is a fixed effect

corresponding to time j , $Group_{ij}$ is an indicator of intervention, and β_2 is the treatment effect (difference in log odds of ART receipt). We test the hypothesis, $H_0: \beta_2 = 0$. The mixed effects model will be extended to allow for covariate adjustment, such as: age, education, and distance from clinic. Separate models will be used to assess each outcome in each population (men, women, infants). For example, ART initiation among pregnant women ($n=1,080$) and then ART initiation among male partners ($n=1,080$). All adult patient models will include depression scale scores as covariates in attempts to control for potential presence of depression symptoms among participant groups. Female-specific models allow for inclusion of covariates unique to pregnant women, such as prior ANC, parity, etc. We also expect the intervention odds ratio to differ between women and their male partners. For infant HIV infection, sensitivity analyses will be conducted to investigate the effect of no EID test result on HIV infection; infants of mothers who did not initiate ART or were not retained in care at delivery will be assigned probabilities of infection (with definitions based on latest research). Then, infant HIV status will be multiply imputed using the Bernoulli distribution and estimates from the multiple regressions will be combined with multiple imputation techniques. An intent-to-treat approach will be employed for all analyses.

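### The entry rule that both partners agree to start ART together is undefined for control clinics, can screen couples differently by arm after allocation, and selects on willingness to start ART

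*Combined protocol and SAP*

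**What the plan says.** The two eligibility lists differ. Section 7b requires that both partners "must agree to enroll in ART together". Section 7c excludes a couple "if one member of the couple is unwilling to enroll in ART or consent to the infant record search", with no mention of doing so jointly.

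Care differs by arm. Section 7f says that "couples on the control arm will receive separate clinical services at the ANC building and the adult HIV clinic, respectively". The intervention description in section 8a offers enrolment in treatment and continuing care as a couple.

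Couples are consented straight after a joint positive test, by a study assistant based at the site (section 8a). The clinics are already listed by arm in Table 2 (section 9). Enrolment is first come, first enrolled up to a fixed number per site (section 7e).

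On outcomes, section 7d claims power to "detect a 30% increase in the proportion of pregnant women who initiate ART from 55% to 71.5" per cent and, in the power calculation, counts people who do not initiate as failures for retention and viral suppression. Section 10 models initiation separately in women and men and applies intention-to-treat throughout. Question 1 in section 6 asks: "Is our intervention idea (partners-based ART services for expectant and post-partum couples) acceptable to expectant couples"?

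**The concern.** Three things follow from the wording.

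- **The test is not clearly the same in both arms.** A couple willing to take ART, but not jointly, passes 7c and may fail 7b. At a control clinic an assistant has little reason to refuse them, because care is separate anyway. At an intervention clinic, agreeing to start together can be taken to mean accepting the joint-care package. Allocation is settled by then, so randomising clinics does not protect against this. An intention-to-treat analysis covers only those enrolled.
- **In both arms, entry depends on a predictor of the outcome.** Stated willingness to start ART comes just before initiation, and initiation feeds retention and suppression. The selection may be strongest in men: the background section reports that fewer than 10% of HIV-infected partners identified in antenatal care enrolled on ART, yet every enrolled man must agree to it. One reluctant man also removes the woman and infant.
- **Question 1 would be put to couples who have already agreed.** The plan provides no count of refusers by arm. Because sites recruit to a fixed number, refusers are replaced, and unequal screening need not show in the final totals.

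**Working it through.** **1. The plan's own figures.** 0.55 × 1.30 = 0.715, so the planned effect is 71.5 − 55 = 16.5 points. Control retention is 0.55 × 0.56 = 0.308, and the target is 0.715 × 0.56 × 1.20 = 0.480. Both agree with section 7d. The statement "With 24 clusters and 45 couples per cluster, we have over 80% power" implies 24 × 45 / 2 = 540 women per arm. About 133 independent women per arm give 80% power (two-sided 0.05), so the claim holds up to an intracluster correlation of (540/133 − 1)/44 = 0.070 on a normal approximation. The plan states no correlation, so the figure is attainable but cannot be confirmed. It is not the issue here.

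**2. Differential screening with no true effect.** Let control clinics admit a share sC of concordant couples and intervention clinics a smaller share sI. Women admitted under either rule initiate at rate a; the extra women admitted only at control clinics initiate at rate b. Then

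spurious difference = a − [sI·a + (sC − sI)·b]/sC = [(sC − sI)/sC] × (a − b).

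All rates below are assumed; the documents give none by arm.

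| sC vs sI | a = 80%, b = 30% | a = 70%, b = 40% | a = 60%, b = 20% |
|---|---|---|---|
| 95% vs 90% | 2.6 points | 1.6 | 2.1 |
| 95% vs 85% | 5.3 | 3.2 | 4.2 |
| 90% vs 70% | 11.1 | 6.7 | 8.9 |

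**3. Bounds using the plan's 55% as the rate among all concordant couples' women (an assumption).**

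- Extreme case, every screened-out woman a non-starter, 95% vs 80% admitted: 0.55/0.95 = 57.9% and 0.55/0.80 = 68.8%, a difference of 10.9 points.
- Same admission rates, screened-out women starting at 30%: (0.55 − 0.05 × 0.30)/0.95 = 56.3% and (0.55 − 0.20 × 0.30)/0.80 = 61.3%, a difference of 4.9 points. If they start at 55%, the difference is zero.
- At least 95% admitted in both arms, worst split 100% vs 95%, all screened-out women non-starters: 55.0% and 0.55/0.95 = 57.9%, a difference of 2.9 points.

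These favour the intervention. The sign reverses if control clinics admit fewer couples.

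**4. The 55% planning rate.** The plan does not say whether 55% describes couples who have already agreed to ART. Its programme figures for women not selected on agreement are higher: 80% (background section) and 87% (section 9). A 30% relative increase is impossible once control initiation exceeds 1/1.30 = 76.9%: 0.80 × 1.30 = 104% and 0.87 × 1.30 = 113%. Holding the plan's 0.56 fixed, control retention would be 0.80 × 0.56 = 0.448 or 0.87 × 0.56 = 0.487. The second already exceeds the 0.48 planned for the intervention arm.

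**The case against.** The best defence has four parts.

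- **Agreeing is not initiating.** A reader might infer that the sample is conditioned on the endpoint itself. The documents do not support that: the rule concerns stated willingness, and section 7d still plans for 45% of control women not starting. This stands. Nor is initiation the named aim. Objective 1 names retention, viral suppression and early infant diagnosis, although initiation is powered, modelled and built into the planned retention rates.
- **The text is the same in both arms.** *Together* could simply mean both partners, and control clinics also offer ART to both. So a reader should not infer that differential selection has been shown; it is a risk created by the wording. The ambiguity remains, because 7b and 7c give different answers for a couple willing to start separately.
- **Enrolment may be near complete.** Section 8a cites enrolment above 95% under a similar protocol. If that held in both arms, the bias would be small (step 3). But nothing says that protocol required both partners to agree to joint ART, and without a refusal count this trial could not show that it matched it. The 11-point figure is a corner case, not an estimate: a willing woman is also excluded when her partner refuses, so many screened-out women could be starters.
- **Rewording does not remove the unmasked, post-allocation approach.** This stands; only the tally makes any remaining imbalance visible.

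On Question 1, section 5 also plans to collect session counts and participant experience, so acceptability does not rest on entry agreement alone. Those data still come only from couples who entered.

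**Conclusion.** The point holds as a defect in the entry rule and its safeguards. The rule is inconsistent between 7b and 7c, is undefined for control clinics, and is applied after allocation with no planned record of who is screened out. It can therefore bias the comparison between arms, and in both arms it narrows the population to couples willing to start ART.

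The size and sign of any bias cannot be derived from the documents. With no true effect, the range is under 3 points (at least 95% admitted in both arms, 55% underlying rate), about 3 to 5 points (95% against 85%), and about 11 points in the extreme case, against a planned 16.5. Separately, the 55% control rate needs a stated population, because above 76.9% the planned relative gain cannot occur.

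A reader might conclude that the ART-willingness criterion must be deleted or initiation dropped as a tested outcome. Neither is required. A couple-based ART trial may reasonably restrict entry this way, provided the test is the same in both arms and the results are labelled accordingly.

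**What to change.** 1. Reconcile 7b and 7c into one criterion that does not depend on accepting joint care, worded and applied identically in both arms.
2. Have the existing site study assistants tally, per clinic, concordant couples tested, approached, eligible and refusing, with reasons. Report these counts and baseline characteristics by arm, and use intervention-arm refusals in answering Question 1. The routine database will not serve, since section 10 says that it cannot link services and holds only HIV-care information.
3. State in 7d whether the 55% describes couples who have already agreed to ART, and reconcile it with the 80% and 87% programme figures.
4. If willingness to start ART stays as an entry condition, report initiation, retention and suppression as applying to couples who agreed to ART.

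The cost is a wording amendment, a short screening tally and a narrower stated population. The tally has to run during recruitment, because refusals not recorded then may be unrecoverable.
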